5.2.1.3 Cohort Expansion

Up to approximately 40 additional subjects will be treated at the RP2D(s) identified in Part 1 for MK-8353, in combination with the fixed dose of pembrolizumab (200 mg IV q3w), to collect more safety and efficacy data at that dose. The population to be enrolled into the cohort expansion (Part 2) is defined in Inclusion Criterion #2 (Section 5.1.2). Several doses and schedules may be explored in Part 2.

5.2.1.4 Tolerability Evaluation Rules and Dose Escalation

The different dose levels of MK-8353 in Arms A and B and optional Arms C and D planned in Part 1 are presented in [Table 4](#).

In Amendment 3 of Protocol 013, the starting dose of MK-8353 is 50 mg bid in Arm A and 50 mg qd in Arm B and optional Arms C and D. Dose escalation will continue as outlined above (Section 5.2.1.2) according to mTPI dose-finding rules. Additionally, doses of MK-8353 at 10 mg and 30 mg could be explored in each arm (Section 5.2.1.2). Concomitant administration of pembrolizumab will be at the fixed dose of 200 mg q3w in all arms and at all dose levels of MK-8353.

Table 4 Dose Levels for MK-8353 + Pembrolizumab in Part 1

Arm A	MK-8353 bid continuous		Pembrolizumab (q3w)
Dose Levels	mg per dose	mg per day	IV Infusion
DL1	350	700	200
DL1A*	50	100	200
DL2A**	50 @ AM + 100 @ PM	150	200
DL3A	100	200	200
DL4A	150	300	200
DL5A	200	400	200
DL6A	300	600	200
Arm B	MK-8353 qd continuous		IV infusion
DL1B	50	50	200
DL2B	100	100	200
DL3B	150	150	200
DL4B	200	200	200
DL5B	300	300	200
DL6B	400	400	200
DL7B	600	600	200
DL8B	900	900	200
DL9B	1200	1200	200
Optional Arm C	MK-8353 qd 1 week on/1 week off		
Dose Levels	mg per dose	mg per day	IV Infusion
DL1C	50	50 for Days 1 to 7, Days 15 to 21, and Days 29 to 35 of a 42-day period (corresponding to 2 cycles of 21 days)	200
DL2C	100	100 for Days 1 to 7, Days 15 to 21, and Days 29 to 35 of a 42-day period (corresponding to 2 cycles of 21 days)	200
DL3C	150	150 for Days 1 to 7, Days 15 to 21, and Days 29 to 35 of a 42-day period (corresponding to 2 cycles of 21 days)	200
DL4C	200	200 for Days 1 to 7, Days 15 to 21, and Days 29 to 35 of a 42-day period (corresponding to 2 cycles of 21 days)	200
DL5C	300	300 for Days 1 to 7, Days 15 to 21, and Days 29 to 35 of a 42-day period (corresponding to 2 cycles of 21 days)	200
DL6C	400	400 for Days 1 to 7, Days 15 to 21, and Days 29 to 35 of a 42-day period (corresponding to 2 cycles of 21 days)	200
DL7C	600	600 for Days 1 to 7, Days 15 to 21, and Days 29 to 35 of a 42-day period (corresponding to 2 cycles of 21 days)	200

Optional Arm D	MK-8353 qd monotherapy run-in then continuous		Pembrolizumab (q3w)
Dose Levels	mg per dose	mg per day	IV Infusion
DL1D	50	50 for Cycle 1, Day 1 to Day 14 (run-in), and Day 1 to Day 21 of subsequent cycles	200
DL2D	100	100 for Cycle 1, Day 1 to Day 14 (run-in), and Day 1 to Day 21 of subsequent cycles	200
DL3D	150	150 for Cycle 1, Day 1 to Day 14 (run-in), and Day 1 to Day 21 of subsequent cycles	200
DL4D	200	200 for Cycle 1, Day 1 to Day 14 (run-in), and Day 1 to Day 21 of subsequent cycles	200
DL5D	300	300 for Cycle 1, Day 1 to Day 14 (run-in), and Day 1 to Day 21 of subsequent cycles	200
DL6D	400	400 for Cycle 1, Day 1 to Day 14 (run-in), and Day 1 to Day 21 of subsequent cycles	200
DL7D	600	600 for Cycle 1, Day 1 to Day 14 (run-in), and Day 1 to Day 21 of subsequent cycles	200

* If 50 mg doses are not tolerable, doses of 10 mg and 30 mg may be explored.
** DL2A (150 mg daily) will be administered as a morning dose of 50 mg and an evening dose of 100 mg of MK-8353.
bid=twice daily; DL=dose level, IV=intravenous, q3w=once every 3 weeks; qd=once daily.

Each individual subject will be assigned to a single dose level of study drug. Intrasubject dose escalation is not allowed. Individual subject dose interruptions and/or dose decreases may be implemented based on toxicity as described in Section 5.2.2; however, dose adjustments should not be made during the DLT evaluation period without discussion with the Sponsor.

The decision to enroll subjects in the next dose level will be made by the Sponsor in consultation with the participating investigators after reviewing the safety and any available PK data of the previous dose level(s).

Subjects may continue on treatment until disease progression, unacceptable toxicity, investigator's decision to withdraw the subject, withdrawal of consent, development of an intercurrent condition precluding further administration of study treatment, pregnancy of the subject, failure to comply with dosing evaluations or other study requirements, or administrative reasons.

5.2.1.5 Definition of Dose-limiting Toxicities

All toxicities will be graded using NCI CTCAE Version 4.0 based on investigator assessment (Appendix 12.7).

The DLT window of observation will be during Cycle 1 for Arms A, B, and C (21 days/3 weeks), and Cycles 1 and 2 for Arm D (35 days/5 weeks).

The occurrence of any of the following toxicities during the DLT window will be considered a DLT, if assessed by the investigator to be possibly, probably, or definitely related to study drug administration:

1. Grade 4 nonhematologic toxicity (not laboratory).
2. Grade 4 hematologic toxicity lasting ≥ 7 days, except thrombocytopenia
 - a. Grade 4 thrombocytopenia of any duration
 - b. Grade 3 thrombocytopenia associated with bleeding
3. Grade 3 nonhematologic toxicity (not laboratory) lasting >3 days despite optimal supportive care.
4. Any Grade 3 or Grade 4 nonhematologic laboratory value if:
 - Medical intervention is required to treat the subject, or
 - The abnormality leads to hospitalization, or
 - The abnormality persists for >1 week.
 - Exceptions:
 - Clinically nonsignificant, treatable, or reversible laboratory abnormalities (eg, liver function tests, uric acid)
5. Febrile neutropenia Grade 3 or Grade 4:
 - Grade 3 is defined as absolute neutrophil count (ANC) $<1000/\text{mm}^3$ with a single temperature of >38.3 degrees C (101 degrees F) or a sustained temperature of ≥ 38 degrees C (100.4 degrees F) for more than 1 hour
 - Grade 4 is defined as ANC $<1000/\text{mm}^3$ with a single temperature of >38.3 degrees C (101 degrees F) or a sustained temperature of ≥ 38 degrees C (100.4 degrees F) for more than 1 hour, with life-threatening consequences and urgent intervention indicated
6. Prolonged delay (>2 weeks) in initiating Cycle 2 due to treatment-related toxicity.
7. Any treatment-related toxicity that causes the subject to discontinue treatment during Cycle 1.
8. Missing $>25\%$ of MK-8353 doses as a result of drug-related AE(s) during the first cycle.
9. Grade 5 toxicity.

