5.2.2.1 MK-8353 Dose Modifications

Criteria for Dose Delay

Except in Cycle 1 in which dosing can be delayed up to 2 weeks, dosing of MK-8353 should be delayed for up to 3 weeks, until the AE is resolved to baseline status or \leq Grade 1 in case of:

- Any treatment-related hematological or nonhematological AE \geq Grade 3
- OR

- Any abnormal nonhematological laboratory value \geq Grade 3 that requires medical intervention, hospitalization, or persists for \geq 1 week, except for a clinically nonsignificant, treatable, or reversible laboratory abnormalities

Any \geq Grade 3 AE of nausea and/or vomiting, or anorexia if left untreated without medical intervention will not require a dose delay.

A reoccurring Grade 2 hematological or nonhematological AE, which in the opinion of the investigator is treatment-related and significant despite medical intervention, should be discussed with the Sponsor prior to any dose delay.

Subjects should be assessed weekly until the AE has resolved to baseline status or \leq Grade 1 and dosing resumes or the subject is discontinued from the study.

If treatment is delayed by more than 3 weeks (or by more than 2 weeks in Cycle 1) because of treatment-related toxicity, study treatment should be discontinued. However, subjects with evidence of clinical benefit may be allowed to continue treatment despite a treatment delay (for any reason) of more than 3 weeks, after discussion with the Sponsor.

Criteria for Dose Modification

Once a dose delay occurs, upon resolution of any treatment-related AE to baseline status or \leq Grade 1, the dose level of MK-8353 for the subsequent doses must be reduced 1 dose level.

Any dose level reduction will be permanent (ie, dose re-escalation is NOT allowed). No more than 2 dose level reductions will be allowed. Subjects who require further dose reductions or dose reductions below DL -1 should be discontinued from the study treatment.

Dose reductions are not permitted during the DLT evaluation period.

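### The exception in DLT criterion 4 overrides that criterion's own triggers, and the other criteria may not recover every related Grade 3-4 laboratory event it removes

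*Combined protocol and SAP*

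**What the plan says.** All references are to the combined protocol and SAP.

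**Section 5.2.1.5, criterion 4.** A related Grade 3 or 4 nonhematologic laboratory value is a DLT under any of three triggers. The first is "Medical intervention is required to treat the subject, or"; the others are hospitalization and persistence beyond 1 week. The exception that follows covers "Clinically nonsignificant, treatable, or reversible laboratory abnormalities (eg, liver function tests, uric acid". It sets no time limit and no grade limit.

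**Section 5.2.1.5, other criteria.** Criteria 1 and 3 (Grade 4, and Grade 3 lasting over 3 days) exclude laboratory values. Criterion 6 is a delay of more than 2 weeks "in initiating Cycle 2 due to treatment-related toxicity". Criterion 7 is "Any treatment-related toxicity that causes the subject to discontinue treatment during Cycle 1". Criterion 8 is missing more than 25% "of MK-8353 doses as a result of drug-related AE(s) during the first cycle". Criterion 9 is death. The window is Cycle 1 for Arms A, B and C, "and Cycles 1 and 2 for Arm D (35 days/5 weeks").

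**Section 5.2.2.1.** MK-8353 is delayed under either of two limbs. The first is "Any treatment-related hematological or nonhematological AE" of Grade 3 or higher, with no laboratory exception. The second covers laboratory values of Grade 3 or higher that meet similar triggers, "except for a clinically nonsignificant, treatable, or reversible laboratory abnormalities".

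**Use of the count.** The DLT proportion is the primary endpoint (Sections 8.1 and 8.4.2). Escalation follows Table 3 (Section 5.2.1.2). DLT rates are pooled across adjacent doses where they violate monotonicity (Section 8.6.2).

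**The concern.** The exception is a list joined by *or*, so one limb is enough. *Treatable* nearly restates the first trigger, and *reversible* fits a value that put the subject in hospital, or lasted over a week, and then resolved. What clearly remains is a value that is significant, untreatable and irreversible. Two investigators could classify the same event differently, and nothing in the section says which wording governs.

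A subject who completes the window with more than 75% of MK-8353 doses stays evaluable (Sections 5.2.1.6 and 8.5.1). An excepted event in such a subject therefore enters the denominator as no DLT; it is not treated as missing. The omission pushes in one direction only, toward staying or escalating.

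Liver tests are the first example in the exception. Section 4.1.2.1 lists liver toxicity in dogs among the main preclinical risks of MK-8353 and says the findings generally recovered within a month. That pattern fits *reversible*.

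**Working it through.** **1. Trigger against exception (criterion 4).**

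| Trigger met | Limb of the exception that can also apply |
|---|---|
| Needs medical intervention | treatable |
| Leads to hospitalization | treatable, or reversible if it resolves |
| Lasts over 1 week | reversible if it resolves later |

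**2. What criterion 8 recovers.** Share missed = doses from the start of the hold to the end of the cycle, divided by doses planned in Cycle 1 (Table 2). Criterion 8 needs more than 25%. This assumes that the hold runs to the end of the cycle.

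| Arm | Planned doses | Latest hold start that meets criterion 8 | One day later |
|---|---|---|---|
| A (bid) | 42 | Day 16: 12/42 = 28.6% | Day 17: 10/42 = 23.8% |
| B (qd) | 21 | Day 16: 6/21 = 28.6% | Day 17: 5/21 = 23.8% |
| C (Days 1-7, 15-21) | 14 | Day 18: 4/14 = 28.6% | Day 19: 3/14 = 21.4% |
| D run-in | 14 | Day 11: 4/14 = 28.6% | Day 12: 3/14 = 21.4% |

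The assumption has some support: Section 5.2.2.1 requires a dose reduction after a delay but bars reductions in the DLT period, so no clear restart exists. It is not certain, because Section 5.2.1.4 allows adjustments after discussion with the Sponsor. If a restart is allowed, a 5-day hold in Arm A or B misses 23.8% wherever it falls.

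**3. Where recovery is uncertain.**

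- *Treated while dosing continues.* Without a hold, criteria 6 and 8 are not met. The second limb of Section 5.2.2.1 repeats the exception, so it need not force a hold. The first limb has no exception, and Section 7.2 counts an abnormal laboratory finding as an adverse event, so it can force one. The two limbs conflict.
- *Late in Cycle 1.* The gap is a value whose hold misses 25% or less of doses, delays Cycle 2 by 2 weeks or less, and does not stop treatment in Cycle 1. The Flow Chart (Arms A, B and C, footnote 5) lets pre-Cycle 2 chemistry be drawn in the 3 days before Day 1. A hold from Day 19 misses 3/21 = 14.3% in Arms A and B.
- *Optional Arm D, Cycle 2.* Criteria 6, 7 and 8 name the start of Cycle 2, Cycle 1 and the first cycle. Cycle 2 is 21/35 = 60% of the window. Of criteria 6 to 9, only criterion 9 reaches a laboratory event there.

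Table 5 permanently stops pembrolizumab for immune-related Grade 3 or 4 liver values. That meets criterion 7 in Cycle 1 only if stopping one drug counts as discontinuing treatment, which is not stated.

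**4. Table 3 reproduced.** Inputs are the target of 0.30, a Beta(1,1) prior and both epsilons of 0.05. With y DLTs in n subjects the posterior is Beta(1+y, 1+n-y). The action is the interval among (0, 0.25), (0.25, 0.35) and (0.35, 1) with the largest posterior probability per unit length. DU is assigned when P(rate > 0.30) exceeds a cutoff. The plan prints no cutoff; 0.95 is an assumption, and 0.90 and 0.92 do not reproduce the grid. For example:

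- 3/3: 1 - 0.3^4 = 0.992, above 0.95, so DU.
- 2/3: 1 - (4 × 0.3^3 - 3 × 0.3^4) = 0.916, below 0.95, so not DU; the printed action is D.

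All 78 cells in rows 0 to 6 match the printed table.

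**5. Effect of omitting one event (printed table, k against k-1 DLTs).**

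| Subjects | Changes in action | Nonzero cells changed |
|---|---|---|
| 3 | 1/3 S to E; 2/3 D to S; 3/3 DU to D | 3 of 3 |
| 4 | 1/4 S to E; 3/4 DU to S | 2 of 4 |
| 5 | 1/5 S to E; 3/5 D to S; 4/5 DU to D | 3 of 5 |
| 6 | 2/6 S to E; 4/6 DU to S | 2 of 6 |

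Every change is toward a less cautious action. At 14 subjects, one event moves the observed rate by 1/14 = 7.1 percentage points.

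**The case against.** The best reply is that the gap is narrow and guarded. The first limb of Section 5.2.2.1 can require a hold for any treatment-related Grade 3 event, and Section 7.1.3.1 requires acceptable laboratory results before each MK-8353 dose. Clinical toxicity that accompanies a serious laboratory value still counts under criteria 1 and 3. Excepted events stay visible: the next dose level opens only after a safety review (Sections 5.2.1.4 and 7.1.2.7), and the Part 2 dose rests on all the data (Section 5.2.1.2). The likely intent is to spare trivial, transient values. The liver argument rests on dog data; the human toxicities described in Sections 2.1 and 4.1.2.1 are rash, nausea, vomiting, diarrhea and fatigue. The sensitivity of Table 3 to one event holds under any DLT definition.

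Much of this stands. Gap one is a conflict between two rules and not a clear permission to keep dosing. The safety review softens the effect on escalation. The dog data cannot show that liver events are being missed in subjects.

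Three things remain. The text does not state the presumed intent. A value that meets a trigger was treated, led to admission or lasted over a week, so it is hard to call trivial. And the safety review does not correct the count that enters Table 3, the pooled estimates and the primary endpoint.

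**Conclusion.** The point holds. Criterion 4 contradicts itself as written, and the DLT count can omit related Grade 3 or 4 laboratory events that needed treatment or admission, or that lasted over a week. This should be fixed. No event rate is given in the documents and none is assumed here, so the size is limited to what one event does to Table 3. The omission is measured against counting every value that meets a trigger.

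A reader might infer four stronger things that the documents do not support.

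- *All late Cycle 1 values and all Arm D Cycle 2 events are lost.* Criterion 6 catches a long delay to Cycle 2, criterion 7 a stop in Cycle 1, and criterion 9 a death.
- *A value treated while dosing continues always escapes.* The first limb of Section 5.2.2.1 may require a hold, which can then meet criterion 6 or 8.
- *Day 16 is a fixed boundary in Arms A and B.* It assumes no restart in the window, which Section 5.2.1.4 does not rule out.
- *DLTs have been undercounted or doses wrongly escalated.* The documents hold no data on this.

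**What to change.** In Section 5.2.1.5, limit the criterion 4 exception to clinically nonsignificant abnormalities. State that a related value meeting the intervention, hospitalization or over-1-week trigger is a DLT even if treatable or reversible, apart from tests exempted by name. Uric acid is a candidate, as are promptly corrected electrolytes if the clinical team so chooses. Naming them stops a minor correction from becoming a DLT by default. Criterion 4 applies across the whole window, so this also covers Cycle 2 of Arm D without rewriting criteria 6 to 8.

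In Section 5.2.2.1, align the second limb for treatment-related values only. That limb is not restricted to related values. Narrowing its exception for all values would force holds for unrelated abnormalities, and a subject without a drug-related event who then took 75% or less of MK-8353 doses would be replaced as nonevaluable (Section 5.2.1.6).

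The cost is a short wording change in two sections by amendment. The DLT count may rise by an amount that the documents do not allow to be estimated. Recorded laboratory events in earlier cohorts need re-checking, so that the pooled DLT-rate estimates, and the preliminary MTD drawn from them, use one definition.

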5.2.1.6 Replacement of Subjects in Dose-limiting Toxicity Period

In order to fully evaluate the safety of the combination therapy in this study, all subjects enrolled must meet the criteria for evaluability for Cycle 1. Subjects are considered nonevaluable and will be replaced if:

- They are enrolled but not treated.

- They discontinue from the trial prior to completing all safety evaluations due to reasons other than drug-related AEs.
- They received <90% of the total pembrolizumab infusion in Cycle 1 (eg, because the infusion had to be discontinued due to an infusion reaction) and did not experience a drug-related event.
- They received $\leq 75\%$ of MK-8353 doses intended for the trial during Cycle 1 and did not experience a drug-related event.
- They must take a prohibited concomitant medication during Cycle 1, unless this medication is used to treat a study drug-related AE.
- They must undergo medical / surgical procedures or have logistical issues not related to study therapy (eg, elective surgery, unrelated medical events) during Cycle 1.

Subjects discontinuing within 21 days (or 35 days for Arm D) of the first dose due to reasons unrelated to study treatment will not be considered evaluable for DLTs and may be replaced. Subjects with a DLT within 21 days (or 35 days for Arm D) of the first dose should not be replaced.

Nonevaluable subjects will not be counted toward the (Part 1 or Part 2) total for DLT evaluation.

Subjects who experience a DLT in the DLT window should be discontinued from the trial. However, if in the opinion of the investigator, the subject is deriving clinical benefit from the study treatment, the subject may be allowed to continue on the trial after discussion with the Sponsor.

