5.6 Rescue Medications & Supportive Care

5.6.1 Supportive Care Guidelines

5.6.1.1 Supportive Care Guidelines for MK-8353

Medications required to treat AEs or concurrent illnesses other than those prohibited in [Table 8](#) are allowed during the study. These include antiemetics, growth factors, and other supportive care medications. Contraceptive medications as described in Section 5.1 are allowed.

Bisphosphonates are allowed for subjects with lytic bone metastases. Antiemetics, including serotonin-receptor antagonists, metoclopramide, prochlorperazine, or thiethylperazine are allowed. Aprepitant is a CYP3A4 inhibitor and should not be used in the study.

Skin rash has been observed in subjects treated with inhibitors of the MAPK pathway and is expected in the current study. It may be representative of an on-target effect of the study medication. Appropriate clinical management of skin rash may be utilized as clinically indicated. An algorithm based on dermatology best practices for other contemporary targeted agents that cause skin toxicity is offered below as guidance to manage skin toxicities seen in subjects being treated on this protocol. The algorithm suggests a step-wise approach to rash management.

- If the rash is NCI CTCAE Grade 1, consider starting with topical steroids (eg, betamethasone), topical antibiotics such as clindamycin gel, or no treatment if the subject is asymptomatic. Use of topical steroid cream with higher potency may be considered early in subjects with moderate rash on the face.

- If the rash is NCI CTCAE Grade 2, continue topical steroid or pimecrolimus cream and consider adding an oral tetracycline or a similar agent.
- If the rash reaches NCI CTCAE Grade 3 or above, dose interruption and/or dose reduction, coupled with the addition of topical steroids is recommended.
- Pruritus of any grade may be treated with an antihistamine, such as diphenhydramine or hydroxyzine hydrochloride.
- Xerosis can be treated with classical emollients.
- Secondary infection may complicate or worsen skin toxicity. To reduce the likelihood of nasal infection, intranasal mupirocin may be considered. Infected rash may be treated with a short course of an oral tetracycline, such as doxycycline. Sun exposure should be avoided in subjects receiving doxycycline or other tetracycline antibiotics.

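### Section 5.2.1.6 replaces an under-exposed subject only if no drug-related event occurred, rather than no DLT, so two kinds of under-exposed subject are counted as DLT-free

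*Combined protocol and SAP*

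**What the plan says.** Section 5.2.1.6 has two exposure tests for Cycle 1. A subject is nonevaluable and replaced after receiving 75% or less "of MK-8353 doses intended for the trial during Cycle 1 and did not experience a drug-related event". The pembrolizumab test is under 90% of the infusion, with an example and the same condition: "eg, because the infusion had to be discontinued due to an infusion reaction) and did not experience a drug-related event". Neither bullet gives a grade or refers to the DLT list. Elsewhere the same section uses the term DLT by name, where it says that subjects with a DLT in the window are not to be replaced. On the effect of the status it says: "Nonevaluable subjects will not be counted toward the (Part 1 or Part 2) total for DLT evaluation".

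Two items in Section 5.2.1.5 bear on this. Item 8 makes it a DLT to miss more than 25% "of MK-8353 doses as a result of drug-related AE(s) during the first cycle". Item 7 reads: "Any treatment-related toxicity that causes the subject to discontinue treatment during Cycle 1". The DLT window is Cycle 1 in Arms A, B and C (21 days) and Cycles 1 and 2 in Arm D (35 days).

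Section 8.5.1 defines the set for DLT evaluation as treated subjects who were observed for 21 days (35 in Arm D) or who had a DLT before then. It sets no minimum exposure.

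**The concern.** An exposure test exists so that a subject who was not adequately treated does not count as evidence that the dose is tolerable. The only reason to keep such a subject is that a DLT occurred anyway. Here any related event is enough to block replacement, including a Grade 1 event that says nothing about dose-limiting toxicity. Mild related events are plausible at these doses. Section 5.6.1.1 says: "Skin rash has been observed in subjects treated with inhibitors of the MAPK pathway and is expected in the current study".

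The primary endpoint is the proportion of subjects with a DLT, and every Table 3 decision uses DLTs over subjects treated. An under-exposed subject kept as DLT-free lowers the observed rate. This matters for a combination in which 3 of 4 subjects had Grade 3 rash at 350 mg bid (Section 2.1).

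**Working it through.** **1. Which under-exposed subjects fall through.**

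*MK-8353.* Compare the replacement threshold (75% or less received) with item 8 (more than 25% missed), using the planned first-cycle doses from Table 2:

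| Schedule | Planned doses | 75% of planned | Most doses received that meets either test |
|---|---|---|---|
| Arm A, bid | 42 | 31.5 | 31 |
| Arm B, qd | 21 | 15.75 | 15 |
| Arm C, Days 1-7 and 15-21 | 14 | 10.5 | 10 |
| Arm D run-in | 14 | 10.5 | 10 |

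Exactly 75% cannot occur, so the two tests select the same subjects. If the doses were missed because of a related AE, of any grade, the subject has a DLT under item 8. If they were missed for another reason and no related event occurred, the subject is replaced. What remains is a subject who missed doses for another reason and also had a related event that was not a DLT.

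*Pembrolizumab.* Item 8 has no counterpart for this drug. An infusion stopped for an infusion reaction is normally a drug-related event, so the bullet cannot apply to its own example. Under Table 6, a Grade 2 reaction stops the infusion. If symptoms do not resolve within 1 hour, dosing is held and the subject is premedicated for the next scheduled dose. Items 1 and 3 of Section 5.2.1.5 need Grade 4, or Grade 3 lasting more than 3 days, and item 7 needs treatment to be discontinued. Such a subject is neither a DLT nor nonevaluable.

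*Arm D.* Both bullets and item 8 refer to Cycle 1 or the first cycle. Arm D gives no pembrolizumab until Cycle 2, although its DLT window covers both cycles. The pembrolizumab bullet therefore has nothing to act on in Arm D.

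**2. Reproducing Table 3.** Inputs from the table: target 30%, Beta(1,1) prior, both epsilons 0.05. For x DLTs in n subjects the posterior is Beta(1+x, 1+n-x). The decision is the interval among (0, 0.25), (0.25, 0.35) and (0.35, 1) with the largest probability per unit length. DU applies if P(rate > 0.30) exceeds 0.95; that cut-off is an assumption, since the documents do not state it. All 78 cells in rows 0 to 6 match, as do rows 9 to 14. Rows 7 and 8 are not fully legible.

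**3. Effect on decisions.** Adding one DLT-free subject to the count moves 12 cells toward escalation, for example 1/5 S to 1/6 E, 2/3 D to 2/4 S, 3/5 D to 3/6 S and 4/6 DU to 4/7 D.

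**4. Effect on the probability of an escalate decision.** Table 3 escalates on 0/3, and on 0/6 or 1/6. Let p be the true DLT rate at full exposure, and let one subject in the cohort be under-exposed and retained. With p = 0.30:

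- n = 3, all fully exposed: 0.7³ = 0.343.
- n = 3, retained subject at zero risk: 0.7² = 0.490.
- n = 3, retained subject at half risk: 0.49 × 0.85 = 0.4165.
- n = 6, all fully exposed: 0.7⁶ + 6(0.3)(0.7⁵) = 0.420.
- n = 6, zero risk: 0.7⁵ + 5(0.3)(0.7⁴) = 0.528.
- n = 6, half risk: 0.85 × 0.528 + 0.15 × 0.7⁵ = 0.474.

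At p = 0.40 the corresponding figures are 21.6%, 36.0% and 28.8% for n = 3, and 23.3%, 33.7% and 28.5% for n = 6.

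If the same subject counts as a DLT under item 8, the effect reverses. At p = 0.30 the probability of an escalate decision is 0% for n = 3 and 0.7⁵ = 16.8% for n = 6.

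**The case against.** A reader might infer that every under-dosed subject with a mild related AE is counted as DLT-free. The documents do not support that. Item 8 makes AE-driven under-dosing of MK-8353 a DLT at any grade, which pushes away from escalation.

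Other provisions narrow the gap further. Lost capsules plausibly fall under a separate bullet of Section 5.2.1.6 that carries no drug-related-event condition: "They must undergo medical / surgical procedures or have logistical issues not related to study therapy". Section 5.8.1 lists noncompliance among the reasons for stopping treatment, and Section 5.2.1.6 treats a subject who stops within the window for unrelated reasons as not evaluable. Grade 3 or 4 infusion reactions lead to permanent discontinuation (Table 6), which is item 7 in Arms A to C. A Grade 2 reaction that resolves within 1 hour may be followed by a restarted infusion, so the dose can still be completed.

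A reader might also infer that the replacement rule will seldom operate because rash is expected. The documents give neither a Cycle 1 rash rate nor an under-exposure rate, so that cannot be said.

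The authors may have meant DLT when they wrote drug-related event. That is possible, but the section uses both terms, and a site applying the text as written would keep these subjects. Escalation is also not mechanical: the sponsor and investigators decide jointly with safety and available PK data (Sections 5.2.1.2 and 5.2.1.4). That can soften the effect, but the DLT counts they review are the same.

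These points limit the scope. They leave the pembrolizumab case and the non-adherent subject who stays on treatment.

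**Conclusion.** The gap is real and limited to two cases: a Cycle 1 pembrolizumab infusion below 90% because of a non-DLT reaction, and more than 25% of MK-8353 doses missed through non-adherence by a subject who stays on treatment and has a coincidental related AE. The first is the firmer, because the bullet's example defeats its own rule.

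One such subject in the cohort, at a true rate of 30%, adds 14.7 percentage points to the probability of an escalate decision at n = 3 and 10.8 at n = 6. If the subject's DLT risk is halved rather than zero, the increases are about 7.3 and 5.4 points. These figures assume one affected subject and a decision taken straight from Table 3. They show what a single misclassified subject does, and are not a forecast of bias in the trial.

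Section 8.5.1 makes the problem wider for the primary endpoint. With no exposure threshold, its DLT set keeps under-exposed subjects even when Section 5.2.1.6 has replaced them.

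**What to change.** Three changes, made together:

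1. In both exposure bullets of Section 5.2.1.6, make the condition 'did not experience a DLT (Section 5.2.1.5)'. An under-exposed subject without a DLT is then replaced, and one with a DLT is still counted. The infusion-reaction example then works.
2. In Section 8.5.1, add the same rule to the DLT-evaluable set: the subject met the exposure thresholds of Section 5.2.1.6, or had a DLT. Without this the primary-endpoint denominator does not change.
3. Reconcile the Cycle 1 wording of the exposure bullets and of item 8 with Arm D's window of Cycles 1 and 2, given that Arm D has no pembrolizumab in Cycle 1.

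This is a counting rule. It changes no dose and no management of infusion reactions. The cost is a short edit in three places and a few more subjects replaced in Part 1.
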